### 3.1.1 Stratification, Randomization, and Blinding

Subjects will be randomized in a 1:1 ratio to either continue or withdraw from MMF. Given the relatively small number of subjects expected per site and the importance of ensuring balance on key disease-defining characteristics an adaptive procedure based on Frane [31] minimization concepts will be used to increase the likelihood of balance in treatment arms. The baseline characteristics that will be considered are study site, disease manifestation (renal disease, which will include subjects who presently have renal disease as well as those who have had renal manifestations in the past, versus non-renal disease, which will include subjects who have never had renal disease), and baseline MMF dose (< 2000 mg per day versus  $\geq 2000$  mg per day).

Subjects and investigational staff responsible for clinical care will not be blinded to the randomized treatment assignment. The cumbersome scheme that would have been needed to maintain the blind required that subjects take different numbers of pills from multiple bottles. Implementation of the scheme would have placed undue burden on the subjects and had a high potential for dosing errors. Knowledge of the assigned treatment also has the advantage of facilitating rapid response in the event of a serious flare.

Unblinding the trial has the potential to impact the estimated rates of disease reactivation, because the definition of this endpoint includes subjective elements. In order to assess the magnitude and direction of the impact on these estimates, a second blinded clinician will also conduct the physical exams scheduled for Weeks 8, 12, 16, and 20. If at Week 20, the subject has a mild/moderate or severe SELENA-SLEDAI flare, the blinded physician should also participate in the Week 24 visit. These time points were selected, because we anticipate that most flares will occur early in the study. The blinded physician will also receive any additional blinded subject records needed to complete the SELENA-SLEDAI and a questionnaire about the need to change medications. This information will be used to compare the rate of disease reactivation among blinded and unblinded assessors.

Statistical and project staff at the SACCC and the DAIT Medical Monitor and Project Manager will be unblinded to individual treatment assignments as well.

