# 8 STATISTICAL CONSIDERATIONS AND ANALYTICAL PLAN

#### 8.1 Sample Size and Power

Sample size justification will focus on the primary endpoint of disease reactivation by Week 60. We anticipate that the risk of disease reactivation will likely increase with MMF withdrawal, and recognize that the acceptable level of increased risk will be highly variable among clinicians and their patients. The planned analyses are designed to provide information to help clinicians make decisions for individual patients with varied levels of risk tolerance. To this end, we will provide the estimated risk of disease reactivation in each arm, but more importantly we will provide the % confidence that the increased risk with MMF withdrawal  $\leq a$ , where a is a specific value for acceptable increase in risk. To facilitate decisions for individual patients, we will provide a table and/or plot showing the confidence levels over a range of values for a.

In deriving an appropriate sample size, we assumed most physicians would want at least 85% confidence that the increase in risk with MMF withdrawal  $\leq a$ , for whatever value of a is selected for an individual patient. As such, we computed, under a variety of scenarios, the probability that the study would yield estimates where the confidence was at least 85% that the increase in risk with MMF withdrawal  $\leq a$  (the acceptable increase in risk). Since this probability is analogous to power for a study designed to test a hypothesis, the term "power" will be used in this discussion.

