In addition to the study size and the selected value of *a*, power depends on two unknowns: the risk of disease reactivation for patients in the MMF maintenance arm and the increase in risk for patients upon withdrawal of MMF. With respect to the former, a preliminary analysis was conducted on observational data from a subset of 49 patients in the Johns Hopkins Lupus Cohort who were on MMF for a minimum of one year. Based on these results, the probability of experiencing disease reactivation (defined for the preliminary analysis as at least one SELENA-SLEDAI-defined flare requiring additional treatment) by month 16 was estimated at 0.10 (95% CI 0.02-0.19) for subjects remaining on MMF. For the sample size and power calculations, we assumed the risk of disease reactivation in the MMF maintenance arm would be on the range of 0.05 to 0.15. There is no preliminary data on the increase in risk with MMF withdrawal, but since patients/clinicians would be more likely to consider withdrawal if the increased risk were low, we evaluated potential increases ranging from 0.05 to 0.15.

Table 8.1 presents power estimates based on simulations for a sample size of 120 eligible subjects randomized in a 1:1 to MMF maintenance or withdrawal. If all other factors are constant, power improves as **a**, the acceptable level of increased risk, increases. However, the relevance of the study results in clinical practice decreases with increasing **a**. For example, the statement, "We are 85% confident that the increased risk with withdrawal of MMF is < a = 0.20" would be useful for those patients willing to accept an increase in risk of **a**  $\ge 0.20$ , but would not be of value for a more risk-averse patient willing to accept, say, an increase in risk of only **a** = 0.10. Unfortunately, the sample size required to achieve 80%

power when  $\boldsymbol{a} = 0.10$  (or below) are not feasible for this study. For example, if  $\boldsymbol{a} = 0.10$ , then under a best case scenario, if the risk of flare is 0.05 in the MMF maintenance arm and the increase in risk with withdrawal is 0.05 (i.e. the risk with MMF withdrawal = 0.10), then the number of patients required for 80% power is 390.

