#### **8.5** Other Statistical Considerations

#### 8.5.1 **Covariates**

Covariates that may be considered include, but are not limited to:

- Age
- Race/ethnicity
- SLE duration
- MMF dose at baseline
- MMF use (cumulative mg-year)
- HCQ use (cumulative mg-year)
- Historical organ involvement
- Serological activity at entry (depletion of C3 or C4, presence of dsDNA antibodies)
- Steroid dose at entry
- Disease activity at entry (m-SLEDAI)
- Disease damage at entry, SLICC/ACR Damage Index (SDI)

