#### 7. ENDPOINT EVALUATION

# 7.1. Overview of Efficacy Analysis Methods

#### 7.1.1. Multicenter Studies

Study subjects were recruited from 19 study sites. Because the endpoint evaluations for this study are largely descriptive, clinical site will not be included as a covariate in the analyses.

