# 7.2.2. Primary Analysis of the Primary Endpoint

The planned analyses for this study are designed to maximize the information available for medical decision-making. The planned analyses are as follows:

Effect estimates and 95% confidence intervals for the risk of disease reactivation by Week 60 in each arm as well as the estimated risk difference (i.e. risk\_MMFwithdrawal - risk\_MMF maintenance) and 95% confidence intervals around the risk difference will be reported using the Kaplan-Meier product-limit estimator.

The observed risk estimates will be used to compute the "% Confidence that the true increase is  $\leq$  a" as a function of values for the "Acceptable increase in risk with withdrawal of MMF (a)". This information will be plotted with values for "Acceptable increase in risk with withdrawal of MMF (a)" on the x axis and estimates for "% Confidence that the true increase is  $\leq$  a" on the y axis. The study will generate a single curve based on the observed risk estimates for the two arms. Physicians with their patients could decide on an acceptable level of increased risk (a) then read from the plot the % confidence that this selected value of a would not be exceeded with withdrawal of MMF. Depending on the level of confidence, they may or may not decide to withdraw MMF.

Version: 1.0 Page 19 of 48

The motivation for the curve comes from the test of non-inferiority with the following hypotheses:

 $H_0$ : the increase in risk with withdrawal of MMF ( $\mathbf{T}$ )  $\geq \mathbf{a}$ , and  $H_A$ : the increase in risk with withdrawal of MMF ( $\mathbf{T}$ )  $< \mathbf{a}$ , where  $\mathbf{a}$  is some value for the acceptable increase in risk.

The  $H_0$  hypothesis would be rejected in favor of  $H_A$  if the upper (1- $\alpha$ ) % confident limit about the estimated risk difference (i.e. risk\_MMFwithdrawal - risk\_MMF maintenance) is less than  $\boldsymbol{a}$ . Then, we could conclude that  $\boldsymbol{T} < \boldsymbol{a}$  with (1- $\alpha$ )% confidence. Physicians and patients who are comfortable with both a risk increase of no more than  $\boldsymbol{a}$  and a confidence level of (1- $\alpha$ )% could conclude that withdrawal from MMF is "not unacceptably worse" than maintenance on MMF.

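### Minimisation balances the arms on renal disease and MMF dose group, but the primary risk difference uses neither; if they predict reactivation, its interval is valid but slightly conservative.

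*SAP*

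**What the plan says.** Protocol 3.1.1 randomises 1:1 with an adaptive procedure whose "minimization concepts will be used to increase the likelihood of balance in treatment arms". It names the factors: "The baseline characteristics that will be considered are study site, disease manifestation" (renal versus non-renal) and "baseline MMF dose (< 2000 mg per day versus" 2000 mg or more).

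SAP 7.2.1 estimates each arm's Week-60 risk by Kaplan-Meier with Greenwood standard errors. SAP 7.2.2 states that "95% confidence intervals around the risk difference will be reported using the Kaplan-Meier product-limit estimator" and builds the confidence curve on that difference. No stratum or covariate enters. SAP 7.2.3 lists a per-protocol analysis, alternative handling of early terminations, and a re-definition for events that rest on immunosuppressant changes alone; none adjusts for a balancing factor. The list of changes in SAP 12 records the move to Kaplan-Meier but says nothing about these factors.

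On covariates, SAP 7.1.1 says "clinical site will not be included as a covariate in the analyses", because the evaluations are largely descriptive. Protocol 8.5.1 is permissive: "Covariates that may be considered include, but are not limited to" a list that contains baseline MMF dose and historical organ involvement. Protocol 8.5.4 and SAP 7.5 allow, but do not require, analyses by renal and dose subgroup. SAP 7.3.2 commits to those subgroups only for the secondary SELENA-SLEDAI flare endpoint.

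**The concern.** When allocation is balanced on factors that predict the outcome, chance differences between the arms on those factors are largely removed by design. An unadjusted variance still counts the between-stratum variation as noise, so it overstates the uncertainty. The protocol chose renal disease and dose because it regards them as defining the disease, and the SAP gives no reason for leaving them out of the primary comparison, although it does give one for site.

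Precision matters here because the trial has no fixed margin and no single test. Its product is a curve of one-sided upper confidence limits, and readers use the part of that curve above the point estimate. A standard error that is too large makes withdrawal look slightly less certain there than the data justify.

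**Working it through.** **Inputs from the documents.** 60 per arm (Protocol 8.1: "power estimates based on simulations for a sample size of 120 eligible subjects randomized in a 1:1" allocation); a one-sided 85% limit ("we assumed most physicians would want at least 85% confidence"), z = 1.036; maintenance risk 0.05 to 0.15 and increase 0.05 to 0.15.

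**Assumptions, not in the documents.** Two independent factors, each split 50:50, each with an odds ratio of 1, 2 or 3 for reactivation, the same in both arms; no censoring.

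**1. Reproduce the plan's figures.** Power = Φ((a − d)/SE − 1.036), with SE = √[(p₀(1−p₀) + p₁(1−p₁))/60].
- Best case, p₀ = 0.05, p₁ = 0.10, a = 0.15: SE = √(0.1375/60) = 0.0479, and Φ(0.10/0.0479 − 1.036) = 85.4%. Table 8.1 gives 85%, and its other filled cells agree within 2 points.
- For a = 0.10 and 80% power, n per arm = (1.036 + 0.842)² × 0.1375/0.05² ≈ 194, or 388 in total against the stated 390.

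Sizing and primary analysis are therefore consistent: both are unadjusted.

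**2. Large-sample effect of adjustment.** Replace p(1−p) by its mean within the four renal × dose strata. For an arm with risk 0.15 and odds ratio 3 per factor, the stratum risks are 0.046, 0.126, 0.126 and 0.302. The mean of r(1−r) is (0.0439 + 0.1101 + 0.1101 + 0.2108)/4 = 0.1187, against 0.1275, so 6.9% of that arm's variance lies between strata. Applying this to both arms:

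| Risk + increase | 95% half-width, unadjusted | OR 2 each | OR 3 each | Power: unadjusted → OR 2 → OR 3 |
|---|---|---|---|---|
| 0.05 + 0.05 | 0.0938 | 0.0930 (−0.9%) | 0.0919 (−2.1%) | a = 0.15: 85.4 → 85.8 → 86.4% |
| 0.15 + 0.10 | 0.1420 | 0.1394 (−1.9%) | 0.1358 (−4.4%) | a = 0.20: 63.4 → 64.4 → 65.8% |
| 0.15 + 0.15 | 0.1470 | 0.1440 (−2.0%) | 0.1400 (−4.8%) | a = 0.20: 35.6 → 36.1 → 36.8% |

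At odds ratio 1 the change is zero.

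**3. Finite-sample check of the unadjusted interval.** With 15 subjects per arm per stratum and 40,000 simulated trials per scenario, 95% coverage was 94.2% to 95.5%.

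**4. Finite-sample check of a weighted estimate.** Weights came from a logistic model of arm on the two factors, with 120 subjects, biased-coin minimisation, and a robust variance that allows for estimating the weights. Standard error relative to unadjusted:
- odds ratio 1: about 0.9% wider;
- odds ratio 2: 0.1% wider to 1.1% narrower;
- odds ratio 3: 0.9% to 3.5% narrower.

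Coverage was 93.9% to 95.6%, and the method never failed.

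Two details decide whether this works. With the weights treated as known, the standard error was 1.000 times the unadjusted one in every scenario. And with no small-sample correction, the variance that allows for the weights was 0.8% narrower even at odds ratio 1, where nothing is gained. The factor √(120/116) = 1.017 (four fitted quantities: two arm risks, two factor effects) turns 0.992 into 1.009.

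**5. Why not a curve per stratum.** Table 8.1 implies 60 × (0.05 + 0.10) = 9 to 60 × (0.15 + 0.30) = 27 events, and SAP 12 reports 8 in the first 80 subjects. At least one arm-by-stratum cell had no event in 94% to 99% of simulated trials at maintenance risk 0.05, and in 34% to 78% at 0.15.

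**The case against.** The case for leaving the plan alone is substantial. The unadjusted interval is valid, the sample size was derived the same way, the trial is declared descriptive, and with so few events a simple two-arm estimate is easy for clinicians to read. The weighted estimate's actual spread was 0.999 to 1.001 times the unadjusted one: the balanced allocation has already delivered the precision, and adjustment only lets the interval report it. All of this stands, and it argues against replacing the primary estimator. It does not argue against a supportive analysis.

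Four stronger readings are tempting and not supported:
- **That the interval is wider than it needs to be.** That depends on the factors being prognostic. The protocol calls them important to the disease but gives no association with reactivation.
- **That SAP 7.1.1 rules out adjusting for renal disease and dose.** The sentence covers site only, and leaving site out is sensible with 19 sites and 120 subjects.
- **That the plan ignores both factors.** They appear among the optional covariates and subgroups, and as committed subgroups for a secondary endpoint. What is missing is a committed adjusted version of the primary risk difference.
- **That lost precision raises every value on the confidence curve.** SAP 7.2.2 runs α from 0 to 0.99. A larger standard error raises the upper limit for α below 0.5, leaves it unchanged at 0.5, and lowers it above 0.5.

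**Conclusion.** The point holds as a minor, conditional one about efficiency, not bias. The arms are balanced on renal disease and MMF dose group, and neither the primary risk difference nor its sensitivity analyses use them. If the factors predict reactivation, the unadjusted interval is slightly conservative. Under assumed odds ratios of 1 to 3 per factor, the adjusted standard error at 60 per arm runs from about 1% wider to about 3.5% narrower. The top end is worth roughly (1 − 0.965²) × 120 ≈ 8 subjects. The largest large-sample power gain at a = 0.15 or 0.20 is about 2.4 points, so few readings of the curve would change.

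These figures rest on equal-sized strata, no dropout and the same odds ratios in both arms. Site was not modelled.

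**What to change.** In SAP 7.2.2–7.2.3, pre-specify a Week-60 Kaplan-Meier risk difference standardised over renal disease and MMF dose group, using inverse-probability weights from a logistic model of arm on the two factors. Specify that:
- the variance accounts for estimating the weights, by stacked estimating equations with a small-sample correction or by a bootstrap that refits the weights in each resample;
- a robust variance that treats the weights as known is not used, since it gives no gain;
- the result is reported beside the unadjusted difference, with its own confidence curve;
- stratum-specific Kaplan-Meier curves are not used, and site stays out.

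The cost is SAP wording and slightly more analysis work. Both factors are recorded at randomisation, so no new data are needed. The downside is an adjusted interval up to about 1% wider if neither factor is prognostic.

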#### 7.1.2. Assessment Time Windows

Allowable visit windows for all scheduled visits are provided in Table 7-1.

 Visit
 Window

 Screening
 -28 to -1

 Baseline
 0

 Weeks 4, 8, 12, 16, 20, 24, 32, 40, 48, 60
 ± 7 days

Table 7-1 Visit Windows

Unscheduled, Flare, and Endpoint visits may also occur throughout the study. All data will be included in analyses, regardless of time of assessment.

# 7.2. Primary Endpoint

# 7.2.1. Computation of the Primary Endpoint

The primary endpoint is the probability in each arm of experiencing clinically significant disease reactivation by 60 weeks after randomization. The 60-week time point is to allow 48 weeks of observation off MMF in the withdrawal arm and minimize dropout, which is likely to occur as the trial lengthens. Clinically significant SLE reactivation requires both:

- 1) A SELENA-SLEDAI\*-defined mild/moderate or severe flare, and
- 2) Increased immunosuppressive therapy on a sustained basis as defined by one of the following criteria:
  - a. Sustained activity: Subject has significant prolonged SLE flare requiring steroid increase/burst to ≥ 15 mg/day prednisone (or its equivalent) for more than four weeks.
  - b. Frequent relapsing/remitting:
    - Subject flares requiring an increase/burst of steroids and is successfully tapered to < 15 mg/day within four weeks, but this occurs on two or more occasions. or
    - ii. Intra-articular, intra-muscular or IV steroids, on more than one occasion.
  - c. Clinical activity of sufficient severity to warrant resumption of or an increased dose of MMF or addition of other major immunosuppressive including azathioprine or methotrexate. Regardless of steroid use, if the investigator observes disease activity of sufficient severity to warrant resumption, addition or increase in dosage of major immunosuppressant in the setting of a SELENA-SLEDAI\*-defined flare, subject has met the primary endpoint.

Version: 1.0 Page 16 of 48

\*ALE06 will typically use a spot urine protein:creatinine ratio rather than a 24-hour urine assessment for the SELENA-SLEDAI. However, if indicated, results from a 24-hour urine collection may be used.

#### SELENA-SLEDAI:

The SELENA-SLEDAI instrument will be completed at baseline and every follow-up visit, including any Flare or Endpoint visits, during the course of the 60 week study period for all subjects. Data for this assessment will be collected on the *Physician's Global Assessment*, *SLEDAI*, and *SELENA Flare & Endpoint Assessment* CRF pages. The SELENA-SLEDAI assesses SLE disease activity and flares based on changes in the SLEDAI score, the Physician's Global Assessment (PGA), medication use (prednisone, NSAIDS, Plaquenil, major immunosuppressives), other disease activity criteria, and hospitalization due to SLE.

Study investigators complete the SLEDAI scale by indicating of presence of 24 SLE disease manifestations during the preceding 10 days. The original SLEDAI instrument includes an evaluation of proteinuria based on the protein:creatinine ratio derived from a 24-hour urine. For this study, the protein:creatinine ratio will typically be derived from the spot urine assessment although a 24-hour urine may be used if the spot urine assessment is not available. Each of the 24 disease manifestations has an assigned weight (see Appendix 14.3). The SLEDAI total score will be computed as the sum of the weights for the items indicated as present. If a component of the SLEDAI (urinalysis or hematological labs only) was missed at a visit, then the missing data will be imputed by using the last observation carried forward approach. If a component of the SLEDAI is missed over consecutive visits, then the subsequent components will not be imputed. If an entire visit was missed, the score will not be imputed.

Mild/moderate and severe SELENA-SLEDAI flares will be defined per the table below. If one or more criteria for a mild/moderate or severe flare have been met, a subject will be considered as having a mild/moderate or severe flare at that study visit.

MILD OR MODERATE FLARE		
	Change in SLEDAI > 3 points	
	New/Worse Discoid, photosensitive, profundus, cutaneous vasculitis, bullous lupus Nasopharyngeal ulcers	Pleuritis Pericarditis Arthritis
		Fever attributable to SLE
	Increase in prednisone, but not to > 0.5 mg/kg/day 	
	Added NSAID or Plaquenil	
	≥ 1.0 increase in Physician's Global Assessment (PhGA), but not to more than 2.5 (on a 3.0 indexed VAS scale—refer to the Physican's Global Assessment located on the Modified SLEDAl Source Document)	
SEVERE FLARE		
	Change in SLEDAI > 12	
	New/Worse CNS-SLE Vasculitis Nephritis Myositis	-0
	Platelet Count < 60,000/ mm  [equivalent to 60 x1	0°/L]

Version: 1.0 Page 17 of 48

Hemolytic anemia with hemoglobin < 7% OR Decrease in hemoglobin > 3%  *Requiring: doubling of prednisone, prednisone > 0.5 mg/kg/day, and/or hospitalization
 Prednisone > 0.5 mg/kg/day 
New Cyclophosphamide (Cytoxan), Azathioprine, Methotrexate, Mycophenolate Mofetil, or hospitalization attributable to SLE
Increase in Physician's Global Assessment (PhGA) to > 2.5 (on a 3.0 indexed VAS scale—refer to the Physican's Global Assessment located
on the Modified SLEDAI Source Document)

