# 1.5.1 **Rationale for the Inclusion Criteria**

Inclusion criteria require patients to have been clinically stable/quiescent for a sustained time period, such that by standard care principles they could consider discontinuation of MMF. The longer sustained period of MMF treatment in the setting of renal involvement reflects the randomized clinical data indicating benefit from MMF maintenance therapy for two or more years. Serological activity will not prohibit entry into the trial, as the predictive capacity of serologies for SLE flare are questionable in the setting of prolonged clinical quiescence [29]. Because we do not wish to have serological activity prohibit trial enrollment, a modification of the SLEDAI, the m-SLEDAI, will be used at screening to determine eligibility. The m-SLEDAI is identical to the SLEDAI except for the exclusion of double-stranded DNA antibodies (anti-dsDNA) and hypocomplementemia [1]. An m-SLEDAI score of < 4 at

screening will allow enrollment in the trial. Minor/transient or nonspecific clinical symptoms are allowed at entry (see Appendix A, *Definition of Mild Disease*), as major immunosuppressant therapy would not be warranted for such symptoms. If the subject is on prednisone therapy for SLE, the dose must have been  $\leq 10 \text{ mg/day}$  (or equivalent dose of alternative corticosteroid) for 12 weeks and stable for 4 weeks prior to randomization as a reflection that the subject has been clinically quiescent (see Section 5.5.2, *Prednisone (or Equivalent)* for the definition of "stable dose").

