12	Hematuria	> 5 red blood cells per high power field. Exclude stone, infection, or other causes.		4					
13	
 
> 0.5 protein:creatinine ratio. New onset or recent increase of more than 0.5 on the protein:creatinine ratio.
 
Proteinuria Note: ALE06 will typically use a spot urine protein:creatinine ratio. If only the 24-hour urine is available, then proteinuria is defined as: ">0.5 gm/24 hours. New onset or recent increase of more than 0.5 gm/24 hours."
 
			4					
14	Pyuria	> 5 white blood cells per high power field. Exclude infection.		4					
15	Rash	Ongoing inflammatory lupus rash.		2					
16	Alopecia	Ongoing abnormal, patchy, or diffuse loss of hair due to active lupus.		2					
17	Mucosal ulcers	Ongoing, oral or nasal ulcerations due to active lupus.		2					
18	Pleurisy	Classic and severe pleuritic chest pain, or pleural rub, or effusion, or new pleural thickening due to lupus.		2					
19	Pericarditis	Classic and severe pericardial pain, or rub, or effusion, or electrocardiogram confirmation.		2					
20	Low complement	Decrease in CH50, C3, or C4 below the lower limit of normal for testing laboratory.		2					
21	Increased DNA binding	> 25% binding by Farr assay or above normal range for testing laboratory.		2					
22	Fever	> 38°C. Exclude infectious cause.		1					
23	Thrombo- cytopenia	< 100,000 platelets/mm  [equivalent to 100 x10  /L]		1					
24	< 3,000 white blood cells/mm 			1					

Total Score (sum of weights next to descriptors marked present):

MII	D OR MODERATE FLARE
	Change in SLEDAI > 3 points
	New/Worse
	
 
Discoid, photosensitive, profundus, cutaneous vasculitis, bullous lupus
 
Nasopharyngeal ulcers
 
Pleuritis
 
Pericarditis
 
Arthritis
 
Fever attributable to SLE
 

	Increase in prednisone, but not to $> 0.5 \text{ mg/kg/day}$
	Added NSAID or Plaquenil
	$\geq$ 1.0 increase in Physician's Global Assessment (PhGA), but not to more than 2.5 (on a 3.0 indexed VAS scale—refer to the Physican's Global Assessment located on the Modified SLEDAI Source Document)
SEV	ERE FLARE
	Change in SLEDAI > 12
	New/Worse 
 
CNS-SLE
 
Vasculitis
 

	• Nephritis
	• Myositis $P_{1} = P_{2} = $

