13	Proteinuria	> 0.5 protein:creatinine ratio. New onset or recent increase of more than 0.5 on the protein:creatinine ratio.  Note: ALE06 will typically use a spot urine protein:creatinine ratio. If only the 24-hour urine is available, then proteinuria is defined as: ">0.5 gm/24 hours. New onset or recent increase of more than 0.5 gm/24 hours."		4
14	Pyuria	> 5 white blood cells per high power field. Exclude infection.		4
15	Rash	Ongoing inflammatory lupus rash.		2
16	Alopecia	Ongoing abnormal, patchy, or diffuse loss of hair due to active lupus.		2
17	Mucosal ulcers	Ongoing, oral or nasal ulcerations due to active lupus.		2
18	Pleurisy	urisy  Classic and severe pleuritic chest pain, or pleural rub, or effusion, or new pleural thickening due to lupus.		2
19	Pericarditis	Classic and severe pericardial pain, or rub, or effusion, or electrocardiogram confirmation.		2
20	Low complement	Low Decrease in CH50, C3, or C4 below the lower limit of		2
21	Increased DNA binding	> 25% binding by Farr assay or above normal range for testing laboratory.		2
22	Fever	> 38°C. Exclude infectious cause.		1
23	Thrombo- cytopenia	< 100,000 platelets/mm  [equivalent to 100 x10  /L]		1
24	Leukopenia	< 3,000 white blood cells/mm  [equivalent to 3 x10  /L] Exclude drug causes.		1

**Total Score** (sum of weights next to descriptors marked present):

Version: 1.0 Page 41 of 48

MIL	LD OR MODERATE FLARE
	Change in SLEDAI > 3 points
	New/Worse
	
 
Discoid, photosensitive, profundus, cutaneous vasculitis, bullous lupus
 
Nasopharyngeal ulcers
 
Pericarditis
 
Arthritis
 
Fever attributable to SLE
 

	Added NSAID or Plaquenil
	> 1.0 increase in Physician's Global Assessment (PhGA), but not to more than 2.5 (on a 3.0 indexed VAS scale—refer to the Physican's Global Assessment located on the Modified SLEDAl Source Document)
SEV.	ERE FLARE
	Change in SLEDAI > 12
	CNS-SLE     Vasculitis     Nephritis     Myositis     Platelet Count < 60,000/ mm³ [equivalent to 60 x10°/L]     Hemolytic anemia with hemoglobin < 7% OR Decrease in hemoglobin > 3%     *Requiring: doubling of prednisone, prednisone > 0.5 mg/kg/day, and/or hospitalization
	Prednisone > 0.5 mg/kg/day
	New Cyclophosphamide (Cytoxan), Azathioprine, Methotrexate, Mycophenolate Mofetil, or hospitalization attributable to SLE
	Increase in Physician's Global Assessment (PhGA) to > 2.5

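### The SLEDAI missing-lab rule omits C3, C4 and anti-dsDNA, so a missed serology panel can create, hide or lose a score-based flare in a serologically active subject

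*SAP*

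**What the plan says.** SAP 7.2.1 builds the score by simple addition: "The SLEDAI total score will be computed as the sum of the weights for the items indicated as present". It then gives three rules for missing data:

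- One missed component: "If a component of the SLEDAI (urinalysis or hematological labs only) was missed at a visit", its most recent earlier value is substituted.
- Repeated misses: "If a component of the SLEDAI is missed over consecutive visits, then the subsequent components will not be imputed".
- A whole visit missed: "If an entire visit was missed, the score will not be imputed".

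Two of the 24 items are serologic, with weight 2 each (SAP 14.3; Protocol Appendix C). Low complement is "Decrease in CH50, C3, or C4 below the lower limit of normal for testing laboratory", and increased DNA binding is "> 25% binding by Farr assay or above normal range for testing laboratory". Protocol 6.3.1 says these tests are needed at every visit for SELENA-SLEDAI scoring. Table 6.1 and Protocol 6.3.5 list them apart from hematology, and Protocol 6.4.1 defines the hematology panel as blood-count parameters only.

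On eligibility, Protocol 1.5.1 states: "Serological activity will not prohibit entry into the trial". Appendix A lists low complement and dsDNA antibodies as acceptable, and screening uses the m-SLEDAI, which leaves both out.

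A SLEDAI change of more than 3 points is by itself a mild/moderate flare, since SAP 7.2.1 needs only one criterion. Neither document says which visit the change is measured against.

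**The concern.** The rule covers every routine lab component of the score except serology, and the trial deliberately admits patients who are positive on serology. Nothing says how an unmeasured serologic item is scored. Taken literally, an item that was not measured cannot be marked present, so it adds nothing. The score then falls when a panel is missed and recovers when it is next drawn, with no change in disease.

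Together the two serologic items are worth 4 points, one more than the 3-point change that must be exceeded, so one missing panel can decide whether a visit counts as a flare. The endpoints most exposed are those for which one visit is enough: any SELENA-SLEDAI flare and the number of flare visits (SAP 7.3.2), and time to first flare (SAP 7.3.3).

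Two sensitivity analyses in SAP 7.2.3 are also exposed. Analysis 2 reclassifies early terminators on a last-visit flare alone. Analysis 3 removes events whose only flare criterion was a major immunosuppressive, so a spurious score rise could keep such a case in and a masked rise could drop one.

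**Working it through.** No sample-size, power or alpha figure depends on this rule, so there is no plan figure to reproduce. The check scores a clinically stable subject by hand.

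**Inputs.** Low complement = 2 and DNA binding = 2 (SAP 14.3). Mild/moderate flare if change > 3; severe if change > 12 (SAP 7.2.1). Carry-forward covers the first missed visit only.

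**Formula.** Score = sum of weights of items marked present. Change = score at this visit minus score at the reference visit.

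**Subject positive on both items, no other activity, five visits (Day 0, then V1 to V4). True score 2 + 2 = 4 throughout.**

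| Panel missed | Unmeasured item handled as | Scores | Flare, change from previous visit | Flare, change from Day 0 |
|---|---|---|---|---|
| V2 | 0 | 4, 4, 0, 4, 4 | V3 (+4) | none |
| V2 and V3 | 0 | 4, 4, 0, 0, 4 | V4 (+4) | none |
| Day 0 | 0 | 0, 4, 4, 4, 4 | V1 (+4) | V1 to V4 (+4 each) |
| V2 | total missing | 4, 4, –, 4, 4 | none | none |
| Day 0 | total missing | –, 4, 4, 4, 4 | none | no change can be computed |
| V2 | carried forward | 4, 4, 4, 4, 4 | none | none |
| V2 and V3 | carried forward once | 4, 4, 4, 0, 4 | V4 (+4) | none |
| Day 0 | carried forward | 0, 4, 4, 4, 4 (nothing to carry) | V1 (+4) | V1 to V4 (+4 each) |

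The last row arises because Table 6.1 has no serology at screening.

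**Subject positive on one item.** Scores 2, 2, 0, 2, 2. The rebound is +2, which is not above 3, so serology alone gives no flare. A real 2-point item at the same visit would bring the change to 4.

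**Severe flare.** The largest serologic artefact is +4, so the > 12 criterion cannot be met by serology alone.

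**Masking.** Suppose new hematuria (weight 4) appears at the visit with the missed panel. True score 4 + 4 = 8, change +4, a flare. With serology scored 0, the score is 0 + 4 = 4 and the change is 4 − 4 = 0 from either reference visit. Hematuria is not in the mild/moderate list of new or worse manifestations, so that list does not pick it up. If hematuria persists, the next score is 8 and the flare is flagged one visit late. If it has resolved, the next score is 4, and the score-change criterion never registers it.

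**What the rows show.** Carry-forward repairs a single mid-study miss. It does not repair consecutive misses or a missed Day 0 panel. Restricting the change to items scored at both visits removes serology from both sides of those comparisons and gives a change of 0 in each.

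**The case against.** The strongest reply is that the SAP never says an unmeasured item counts as absent. Protocol 8.5.5 sets a general default of no imputation, with departures to be stated in the SAP. On that default the total would be missing and no false flare arises. This stands as far as it goes: zero-scoring is an inference from the summing rule. But the SAP leaves the score unimputed explicitly only for a whole missed visit or a repeated miss, and it does not say whether the total then becomes missing. A missing total also has a price, since the score-change criterion disappears at that visit. If the Day 0 panel is missed and change is from Day 0, it disappears for the whole of follow-up.

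Second, a mid-study miss creates a flare only if change is read from the previous visit. That is correct, and the reference visit is unstated.

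Third, hematological labs might be read loosely as any blood test. The documents' own panel definitions point the other way.

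Fourth, a reader might extend the point to a second consecutive missed urinalysis, because each urine item weighs 4. This largely fails. Entry requires m-SLEDAI below 4, so no one has a urine item at screening, and a subject who acquires one later has already had a genuine rise of 4. What remains is repeat flare-visit counts and items acquired between screening and Day 0.

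Fifth, missed panels may be uncommon, because this draw is in the first-priority tier of Protocol 6.3.5. Nothing in the documents suggests they would differ by arm. Both points stand and limit the importance of the issue.

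**Conclusion.** The gap is real and worth closing, but its reach is limited. For a subject positive on both serologic items, one missed panel can add a spurious +4 against a threshold of more than 3, hide a real +4, or remove the score-change criterion. Which of these happens depends on two choices the SAP does not make: how an unmeasured item is scored, and which visit is the reference.

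The exposed results are any SELENA-SLEDAI flare, time to first flare and flare counts, all exploratory and descriptive, together with sensitivity analyses 2 and 3.

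A reader might infer that the primary result is materially biased. The documents do not support that. Reactivation also requires increased therapy, and a prednisone increase or a new major immunosuppressive usually meets a flare criterion by itself (SAP 7.2.1). The residual routes are narrow: repeated injected steroids, or an event date moved earlier.

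A reader might also infer that every biomarker analysis is affected. SAP 7.4.1 and 7.4.2 also use Baseline and Week 20 and group subjects by clinically significant reactivation. SAP 7.4.3 rests on Baseline and Week 60, with the flare visit only if needed. Only the first-flare and pre-flare time points are exposed.

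The number of affected subjects cannot be computed: the documents give neither the frequency of missed panels nor the share of subjects positive on both items. Any headcount would rest wholly on assumed rates and would have to discount subjects who truly flare anyway. SAP section 12 says flare rates exceed 10%.

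**What to change.** Amend SAP 7.2.1 in three sentences:

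1. Extend the one-visit carry-forward to C3, C4 and anti-dsDNA, on the same terms as urinalysis and hematology.
2. Where an item is still unmeasured (consecutive misses, or a missed Day 0 panel), compute the change in SLEDAI only over items scored at both visits, rather than counting the item as absent or discarding the total.
3. State whether the change is measured from the previous visit or from Day 0.

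The cost is a little programming and no new data; Protocol 8.5.6 allows revised plans. There are two downsides. A true serologic change at a missed visit is picked up one visit later. Where the second rule applies, serology drops out of that comparison; if Day 0 is the reference and its panel was missed, it drops out for all of that subject's follow-up.
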